11.2 Statistical Analysis

All analyses will be intent-to-treat. All subjects randomized will be evaluable for safety and all subjects that have both a pre and post specimen are evaluable for efficacy. Primary analysis of efficacy will be performed on all evaluable subjects and secondary analysis will be done on those subjects who received at least 6 months of study medication and were confirmed as being in the follicular phase for both RPFNA procedures. From our experience we have very little missing data; however, if the missing data rate is above 5%, we will use multiple imputation to impute these values to perform the primary and secondary analyses.

The primary outcome will be change in Ki-67 (percent of cells expressing Ki-67) from baseline to 12 months. The two-sample t-test will be used to compare the change in Ki-67 between the SDG

and placebo groups. Any difference in baseline values of Ki-67 between the two groups would be due to chance, however, if there is a significant difference, then analysis of covariance adjusting for baseline values will be performed. Due to potential skewness in these variables we will assess whether or not the Central Limit Theorem may be assumed. Given the sample size the existence of an extremely high degree of skewness would require the use of the Wilcoxon Signed Rank test.

For the secondary endpoints, similar methods as above will be used to compare the treatment and control groups at two time points for all markers, i.e., serum hormones and clinical laboratory tests. We will also correlate change in the primary biomarker Ki-67 with change in other markers (e.g., bioavailable estradiol, cytokines, RTqPCR results) using Pearson's correlation coefficient. Again, if there exists a high degree of skewness in these variables, Spearman's correlation will be utilized.

Multiple regression analysis will also be used to investigate whether changes in Ki-67 are due to variables other than treatment effect (e.g., age, cytromorphology, Gail risk; as well as the predictive effect of other biomarkers on modulation of Ki-67). Best subsets and stepwise approaches will be employed while controlling for treatment group.

For comparison of moderate or worse toxicities we will consider grade 3 toxicity or premature trial discontinuation as the critical events. The prevalence of events in the SDG vs. the placebo arm will be examined by Fisher's exact test.

Evaluation of agent-induced hormonal changes - We will examine whether SDG has any effects on serum levels of bioavailable estradiol, and testosterone, determined at baseline and after 12 months of study medication. We will determine whether addition of SDG alters the frequency or length of menstrual cycles. Effects on follicular reserve will be evaluated with anti-mullerian hormone in a sub-cohort of pre-menopausal women between ages 21 and 35 at study entry. Antimullerian hormone (AMH) is one of the earliest and most sensitive measures of follicular reserve declines for approximately 10 years before the cessation of menses. A distinct advantage for trial purposes is that it does not vary with day of menstrual cycle [119].

Adverse Events and Quality of Life – Change from baseline to 12 months will be assessed for mastalgia (expected in 30-50% of subjects at baseline), menstrual cycle and follicular reserve, and quality of life, as a function of SDG intake, plasma lignan levels and urinary lignan excretion. We will use the breast pain questionnaire (BPQ), which is a modified short form of the McGill Pain questionnaire (SF-MPQ) to assess breast discomfort and the Breast Cancer Prevention Trials (BCPT) Symptom Checklist to monitor quality of life

Correlative analyses will be performed with plasma and urine ENL and total lignans as the independent variable, with modifying variables of baseline BMI age and specific SNPs such as CYP17.

Since this is a phase IIB trial, the power and sample size for the primary endpoint was determined with a two-sided type I error rate of 5%. All subsequent secondary, tertiary and exploratory analyses will also be tested with a two-sided type I error rate of 5%. This may result in an elevated false positive rate for these secondary and tertiary analyses, however, since this is a Phase IIB study, we felt to control the type I error rate for the secondary, tertiary and exploratory analyses would be too conservative.

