1.0 OBJECTIVES

The overall objective is to determine whether the natural flaxseed lignan, secoisolariciresinol diglycoside (SDG), in amounts providing plasma lignan levels associated with reduced breast cancer risk, will favorably modulate risk biomarkers for breast cancer development. This will provide biologic evidence of SDG's potential for breast cancer chemoprevention. Based on a positive pilot study in which both Ki-67 and the proportion of women with atypical cytomorphology was reduced with 12 months of SDG 50 mg/day, a randomized, placebo-controlled clinical chemoprevention trial will be conducted wherein pre-menopausal women at increased risk for the development of breast cancer will receive Brevail® (200 mg, equivalent to 50 mg of SDG) or matched, blinded placebo for 12 months. A total of 242 subjects will be accrued, randomized 2:1 to SDG vs placebo, with the goal of achieving 220 subjects completing study and evaluable for biomarker change.

The primary objective is to determine if women randomized to 12 months of SDG exhibit greater change in the proportion of breast epithelial cells expressing the proliferation marker Ki-67/MIB-1 in hyperplastic benign breast tissue than do women randomized to placebo.

Secondary objectives are:

- 1) to determine if 12 months of SDG is associated with favorable modulation of other risk biomarkers including cytologic atypia, and serum levels of bioavailable estradiol and testosterone, IGF-I:IGFBP-3 ratio, c-peptide, adiponectin, and leptin.
- 2) to determine if Ki-67 and modulation of other risk biomarkers is correlated with change in blood or urine lignans.
- 3) to determine impact or potential impact on quality of life as measured by the BPQ breast pain questionnaire (a modified McGill Pain questionnaire), The Breast Cancer Prevention Trial (BCPT) Symptom Checklist a menstrual diary for cyclicity and cycle length for women not on cycle modulating contraceptives; and antimullerian hormone (AMH), a measure of follicular reserve.

An exploratory objective is to interrogate SDG's mechanism of action through measurement of changes in hormones, growth factors, gene expression, adipokines and cytokines and proteomic signatures.

The overriding hypothesis is that biomarkers assessed both in serum and in hyperplastic breast tissue obtained by RPFNA from high risk pre-menopausal women will be favorably modulated by 12 months of SDG without negatively affecting quality of life.

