4.5 Screening, Consent and Enrollment Process

- 4.5.1 Cohort and Accrual: Potential subjects will be screened in the Breast Cancer Prevention Center at the University of Kansas Medical Center (KUMC), Kansas City, Kansas; and at similar high risk clinics at collaborating institutions. Recruitment will be conducted over approximately 4.5 years for a total accrual of n=242.
- 4.5.2 Consent at KUMC: At KUMC, potential subjects will sign KUMC HSC#4601 consent for screening RPFNA procedure; subjects qualifying for randomization will sign the trial specific consent document.
- 4.5.3 Consent at collaborating sites: Collaborating sites may use the trial specific consent prior to screening RPFNA for obtaining biospecimens for baseline assays, or may use a separate approved research/clinical consent for that purpose.
- 4.5.4 All prospective subjects undergoing RPFNA for screening at collaborating sites will be registered in a site screening log by the site study coordinator or principal investigator. The study coordinator will assign a unique identifier from a pre-designated series specific to that institution. This identifier, which will include subject initials, serves as the subject "name" for screening purposes and along with the date will be attached to all subject related biospecimens sent to KUMC. A screening checklist will also accompany the screening RPFNA specimen. This will also be used for pre-enrollment blood, urine questionnaires, and data collection. No protected health information should be attached to these items.
- 4.5.5 Subjects may not be stratified and randomized until they have completed the entire eligibility process including RPFNA and collection of baseline biospecimens, and the site study coordinator has received confirmation from KUMC that the subject is tissue eligible, and for non-menstruating women that the RPFNA was performed in the follicular phase.
- 4.5.6 The RPFNA results provided to the site will include the cytomorphology descriptor (non-proliferative, hyperplasia, or hyperplasia with atypia), cytology index score and Ki-67 percent positive cells; as well as a statement that the subject is or is not eligible on the basis of RPFNA to be randomized and enrolled.

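### Section 11.2 says intent-to-treat but analyses only women with both specimens, and its 5% imputation rule names no denominator, so two primary analyses are possible

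*Combined protocol and SAP*

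**What the plan says.** Section 11.2 makes four statements that bear on who is in the primary analysis.

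- The principle: "All analyses will be intent-to-treat".
- The definition: "all subjects that have both a pre and post specimen are evaluable for efficacy".
- The primary set: "Primary analysis of efficacy will be performed on all evaluable subjects". A secondary analysis is limited to women with at least six months of study medication who were "confirmed as being in the follicular phase for both RPFNA procedures", so it too needs both aspirates.
- The exception: "if the missing data rate is above 5%, we will use multiple imputation to impute these values to perform the primary and secondary analyses".

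An unadjusted two-sample t-test on change in Ki-67 is the primary test. The same section argues that "Any difference in baseline values of Ki-67 between the two groups would be due to chance", and adjusts for baseline by analysis of covariance only if the difference is significant.

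Section 1.0 plans 242 randomised women, "with the goal of achieving 220 subjects completing study and evaluable for biomarker change". Section 3.0 assumes 10% dropout. Section 4.5.5 fixes the order of events: "Subjects may not be stratified and randomized until they have completed the entire eligibility process including RPFNA and collection of baseline biospecimens". Section 5.1 asks women who stop early to return for biomarker re-assessment.

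**The concern.** Every randomised woman has a baseline specimen, so the both-specimens condition in effect excludes women with no post-treatment specimen. An analysis that omits them is not intent-to-treat in the usual sense. The imputation rule might bring them back, but that depends on what the 5% is counted over, and no section says.

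At stake is whether the primary result comes from about 220 complete cases or from 242 women with about 22 values imputed. If that is left open, it can be settled once the data, or the amount of missing data, are known. A related weakness is that the argument from chance about baseline differences holds for all randomised women, but not necessarily for those who remain after dropout.

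**Working it through.** **Inputs from the documents.** 242 randomised, 2:1, 220 evaluable (Section 1.0); 10% dropout (3.0); difference 2.5, SD of change 6, power 83% (11.1); two-sided 5% level (11.2); pilot 49 accrued and 45 evaluable (2.4.4).

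**The plan's power reproduces.** SE = 6 × √(1/73.3 + 1/146.7) = 0.858; 2.5/0.858 = 2.91; power = Φ(2.91 − 1.96) = 83.0%. The t distribution with 147 and 73 women gives 82.6%.

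**Expected loss.** Plan: (242 − 220)/242 = 9.1%, or 10% as stated. Pilot: 4/49 = 8.2%, exact 95% interval 2.3% to 19.6%.

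**Reading 1: 5% of randomised women.** 0.05 × 242 = 12.1, so 13 or more missing triggers imputation.

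| True loss | P(at least 13 of 242) |
|---|---|
| 3% | 3% |
| 4% | 17% |
| 5% | 44% |
| 6% | 70% |
| 8.2% (pilot) | 96.3% |
| 9.1% (plan) | 98.8% |
| 10% (plan) | 99.7% |

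**Reading 2: 5% of evaluable women.** A woman without a post-treatment specimen is outside the set, so dropout contributes nothing. 0.05 × 220 = 11, so the rule acts on Ki-67 only if 12 or more women with both specimens have no usable value. The documents give no unscoreable rate; the rates below are assumptions.

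| Assumed unscoreable rate | P(at least 12 of 220) |
|---|---|
| 1% | <0.01% |
| 2% | 0.2% |
| 3% | 3.5% |
| 4% | 17% |
| 5% | 42% |
| 6% | 67% |
| 7% | 85% |

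**How far the two analyses differ.** Simulated trials used 161 and 81 women, true effect 2.5 and SD of change 6. Baseline was skewed with mean 6.4 (Section 3.0). Assumed: baseline SD 4.5 or 5.7, and slope of change on baseline −0.5.

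- Loss completely at random: no bias. The unadjusted completer and imputed analyses reach different verdicts in 2.4% to 3.5% of trials; if both are baseline-adjusted, in 0.8% to 2.1%.
- Dropout in the same direction in both arms, or merely unequal in amount (12% against 3.3%): no bias.
- Dropout dependent on baseline Ki-67 in opposite directions by arm (assumed log-odds per SD):

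| Log-odds | Completer t-test | Plan's conditional rule | ANCOVA triggered |
|---|---|---|---|
| ±0.2 | 2.38–2.43 | 2.43–2.45 | 6–7% |
| ±0.4 | 2.29–2.30 | 2.36–2.41 | 9–10% |
| ±0.8 | 2.06–2.16 | 2.28–2.33 | 21–22% |

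Baseline-adjusted completers and the imputed analysis both give 2.47 to 2.52, against 2.47 to 2.51 with no loss. At ±0.8 the conditional rule leaves about half the bias: 2.50 − 2.33 = 0.17 of 2.50 − 2.16 = 0.34 at SD 4.5, and 2.49 − 2.28 = 0.21 of 2.49 − 2.06 = 0.43 at SD 5.7. At ±0.2 more than half remains, but of a much smaller bias.

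**Gain from adjusting anyway.** At slope −0.5 the residual SD falls by the factor √(1 − (0.5 × SD/6)²), a reduction of 7% at baseline SD 4.5 and 12% at 5.7.

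**The case against.** The strongest defence is that 11.2 is loosely worded but workable. Over randomised women, the text reads as a default with an exception, and an exception that is expected to apply does not contradict its default. Over evaluable women, intent-to-treat may mean only that women are analysed as assigned whatever their adherence, in contrast to the exposure-restricted secondary set. Sections 1.0, 3.0 and 11.1 all plan on the same 220 evaluable women. This stands to the extent that a reader who infers that some sentence of 11.2 must fail on any reading goes too far. It does not supply the denominator.

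A reader might also infer that the rule is idle when counted over evaluable women. The documents do not show that. Evaluable requires a specimen, not a usable score; Appendix 1 (5.3) needs at least 500 ductal cells for scoring, and Appendix 1 (5.2) reports good RNA/cDNA from only 83% of microdissected samples. Missing marker values among evaluable women could therefore exceed 5%. What is certain is that dropout cannot trigger the rule on that reading.

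The third objection is that the simulated bias comes from the conditional baseline adjustment, not from the denominator, and needs opposite-direction dropout in a trial where women and site staff are blinded. That is correct, and so is the point that the inputs are soft. Section 11.1 gives the pilot baseline average as 4%, not 6.4%, and a baseline SD of 5.7 gives only about a 6% chance that all 45 pilot women fall at or below the reported maximum of 16.8%.

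Two further defences carry less weight. Section 11.2 expects very little missing data, but the plan's 10% and the pilot's 8.2% both exceed its trigger. Section 5.1 may recover some early stoppers, but 220 of 242 is already the planned evaluable count.

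**Conclusion.** The point holds as one of specification. The intent-to-treat label does not describe the set defined for the primary analysis, and the 5% rule leads to different primary analyses depending on an unstated denominator. Over randomised women, imputation is the expected primary analysis at the planned or pilot loss; at a true loss of 4% or less it probably would not be triggered. Over evaluable women, about 22 randomised women are left out whatever happens.

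The expected effect on the result is small. A reader might infer that the planned comparison is biased or underpowered, but the documents do not support either: random loss gives no bias, and the 83% power is computed on 220 women and reproduces. Bias requires dropout tied to baseline Ki-67 in opposite directions by arm, which the documents neither support nor exclude. Its simulated size rests on the assumed baseline SD and slope and on the 6.4 mean. Where it arises, adjusting only after a significant baseline difference leaves roughly half or more of it. Unconditional adjustment removes it in either analysis set. The change should be made because it is nearly free and closes a choice that could otherwise follow the data.

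**What to change.** Before unblinding, amend Section 11.2 as follows.

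1. Adjust the primary comparison of change in Ki-67 for baseline Ki-67, whatever a baseline test shows.
2. Name one primary set and drop the 5% switch. Either take all randomised women as assigned, keeping observed post-treatment specimens from early stoppers and multiply imputing missing 12-month Ki-67 on at least arm and baseline Ki-67; or take the evaluable women, described as such and not as intent-to-treat.
3. Report the other set as a named sensitivity analysis.

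An optional further sensitivity analysis imputes SDG dropouts from placebo. It understates the effect if those women keep the benefit (2.5 × 220/242 = 2.27), so it should not be primary.

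The cost is SAP wording, modest programming and replacing the stated t-test with analysis of covariance. No new data are needed. The all-randomised interval will differ slightly from the evaluable-only one.

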3.0 SUMMARY OF STUDY PLAN

The favorable outcome of the pilot study suggests progression to a Phase II multi-institutional placebo-controlled trial of 12 months of Brevail® (50 mg SDG) in moderate and high risk premenopausal women. Modulation of Ki-67 in women with baseline Ki-67 of 2% or greater in hyperplastic tissue is the primary endpoint rather than normalization of atypia, so as to limit the number of women who would need to be screened by RPFNA to 2-3 for every woman going on trial (vs. 4-5 if all had to have atypia). Other risk biomarkers will be measured, as well as impact on quality of life, change in breast pain in those with mastalgia at baseline, and surrogate markers of fertility. These considerations will be important for eventual uptake of SDG as a prevention agent. Mechanisms of action will also be explored. Similar eligibility criteria are used as in the pilot study, where the average percentage of cells expressing Ki-67 at baseline was 6.4% (median 4%) with an average change of -3.7% with a common standard deviation of 5.5%.

The study eligibility is being altered approximately 2.5 years after study start to allow inclusion of women on oral contraceptives. This will both widen application of results should they be positive and is expected to at least double the rate of accrual. Assessment of difference in change in Ki-67 between women randomized to SDG versus placebo can be accomplished with a 2:1 randomization of 242 women. Assuming a dropout rate of 10%, with 220 evaluable subjects there will be 83% power to detect a 2.5% reduction in Ki-67 for the treatment group compared to no reduction in the control group; this will be our primary endpoint. This is based on an assumption of a common standard deviation of 6% for change in Ki-67 in both the no oral contraceptive and oral contraceptive groups and a Type I error rate of 5%

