11.0 STATISTICAL METHODS

The study is a Phase II, double-blind, randomized, placebo-controlled clinical trial to assess the potential efficacy of SDG as a chemopreventive agent, as measured by changes in proliferation index (Ki-67) between baseline and 12 months. Secondarily, the study will evaluate other pharmacodynamic properties of the agent and assess which biomarkers, if any, are modulated. Side effects, adverse events, and quality of life will also be assessed.

Standard randomization strategies will be employed. Institutional site and whether the woman is on or not on oral contraceptives will be the only stratification factors, so that each site can be provided with a unique randomization schedule at initiation. All eligible subjects will be randomly assigned to SDG or placebo in a planned 2:1 ratio.

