11.1 Sample Size and Power

The primary outcome of interest is efficacy of SDG relative to the placebo, thus the pre- to post-treatment change in a proliferation index (percent of cells expressing Ki-67) is the basis of the power analyses. From our pilot study, the average percentage of cells expressing Ki-67 at baseline was 4%, and the average change in percent of cells expressing Ki-67 was a 2.4% reduction, for subjects meeting similar eligibility requirements as used in this trial.

A 2:1 randomization of 220 evaluable subjects will provide 83% power to detect a 2.5% reduction in Ki-67 for the treatment group compared to no reduction in the control group; this will be our primary endpoint. This is based on an assumption of a common standard deviation of 6% for change in Ki-67 in both groups and a Type I error rate of 5%. Within the target of 220 evaluable subjects, we expect to recruit 72 women taking oral contraceptives (OC) and 148 women not taking OCs. Because the efficacy of SDG is unknown for OC users, we considered different scenarios and evaluated the average effect in the SDG arm and the corresponding power. For 0-70% efficacy of SDG among OC users, the respective average Ki-67 reduction range from 1.7% to 2.3% will result in a statistical power ranging from 50% to 76%.

Ki-67 reduction in SDG arm (non-OC)	Efficacy of SDG in OC	Ki-67 reduction in SDG arm (OC)	Ki-67 reduction in SDG arm (OC & non-OC avg.)	Power
2.5%	0%	0%	1.7%	50%
2.5%	20%	0.5%	1.8%	55%
2.5%	50%	1.3%	2.1%	68%
2.5%	70%	1.8%	2.3%	76%
2.5%	100%	2.5%	2.5%	83%

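### Baseline Ki-67 enters the primary analysis only after a significant baseline test, and the randomisation strata never enter it, so available precision is lost

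*Combined protocol and SAP*

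**What the plan says.** Section 11.2 compares change in Ki-67 from baseline to 12 months between arms with a two-sample t-test. It says that a baseline difference between arms would be due to chance, but continues: "if there is a significant difference, then analysis of covariance adjusting for baseline values will be performed". No significance level is given for this baseline test.

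Section 11.0 says that "Institutional site and whether the woman is on or not on oral contraceptives will be the only stratification factors". Section 11.2 puts neither factor in the primary comparison. A later paragraph of 11.2 plans multiple regression by best subsets and stepwise selection to look for other explanations of change. It names age, cytomorphology and Gail risk among its examples, but not baseline Ki-67, OC use or site.

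The sample size in Section 11.1 rests on the unadjusted comparison: "A 2:1 randomization of 220 evaluable subjects will provide 83% power to detect a 2.5% reduction in Ki-67 for the treatment group". It also recognises that OC use may matter: "Because the efficacy of SDG is unknown for OC users, we considered different scenarios".

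**The concern.** In a randomised trial a baseline test can only detect chance imbalance. It carries no information on whether baseline predicts change, which is what decides whether adjustment reduces the error variance.

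There is good reason here to expect that it does. Entry requires Ki-67 of at least 2% (4.4.3), and 2% is the median in comparable women (2.4.3). Women are therefore drawn from the upper half of the distribution, where regression to the mean is likely. There is also a floor: a woman who enters at 2% cannot fall by the 2.5-point design effect, while one at 16.8%, the pilot maximum (2.4.4.2), can.

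Three things are at stake:

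- **Power.** The change score carries variance that baseline could remove.
- **Uncorrected imbalance.** A chance difference just short of significance stays in the estimate, because the arm that starts higher tends to fall more.
- **Choice of model.** Which of two models gives the primary result is left to the baseline data.

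Leaving out the strata also makes the standard error too large if site or OC use is prognostic.

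**Working it through.** **Inputs.** 220 evaluable women at 2:1, difference 2.5 points and SD of change 6 (11.1); two-sided 5% (11.2). The documents do not give the correlation *r* between baseline and 12-month Ki-67, so I take *r* = 0.3, 0.5 and 0.7, with equal variances at the two times.

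**Step 1: the plan's own figure.** Standard error = 6 × √(1/146.67 + 1/73.33) = 6 × 0.1430 = 0.858. Power = Φ(2.5/0.858 − 1.96) = Φ(0.953) = 83.0% (82.6% by noncentral t). The stated 83% reproduces. The 0% OC-efficacy row of the 11.1 table also reproduces: an average effect of 1.7 gives 50.8% against the stated 50%.

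**Step 2: always adjust for baseline.** With equal variances, residual SD = 6 × √((1 + *r*)/2). The sample-size equivalent of the gain is 2/(1 + *r*).

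| *r* (assumed) | Residual SD | Power at 2.5 | Power at 1.7 | Equivalent to enlarging the unadjusted trial by |
|---|---|---|---|---|
| unadjusted | 6.00 | 83.0% | 50.8% | – |
| 0.3 | 4.84 | 95.1% | 69.0% | 54% |
| 0.5 | 5.20 | 92.0% | 62.8% | 33% |
| 0.7 | 5.53 | 88.5% | 57.5% | 18% |

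The 1.7 column shows the gain from baseline adjustment when the true average effect is smaller. It is not a gain from adjusting for OC use.

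**Step 3: unequal variances.** Over the same range of *r*, power at 2.5 points is 97 to 99% if the 12-month SD is 0.75 times the baseline SD, and 83 to 88% if it is 1.5 times. The gain vanishes only when the slope of 12-month on baseline Ki-67 equals 1.

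**Step 4: the rule as written.** Simulation of 20,000 trials per setting (147 against 73, difference 2.5, baseline test at an assumed 5%) gave 84.1%, 83.6% and 83.6% power for *r* = 0.3, 0.5 and 0.7. ANCOVA in every trial gave 94.6%, 91.8% and 88.2%. The baseline test is positive in only about 5% of trials, so the rule almost always ends in the t-test.

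**Step 5: imbalance that the test misses.** With equal variances, the correlation between baseline and change is −√((1 − *r*)/2). Take *r* = 0.5:

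- The baseline SD is 6/√(2 × 0.5) = 6, so the standard error of the baseline difference is also 0.858.
- A baseline t of 1.9 is not significant. It corresponds to a difference of 1.9 × 0.858 = 1.63 points.
- The change slope is *r* − 1 = −0.5, so the unadjusted estimate moves by 0.5 × 1.63 = 0.82 points, about a third of the design effect.

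Under no treatment effect and a baseline t of 1.6, the conditional rejection rate of the t-test is about 10%, 9% and 8% for *r* = 0.3, 0.5 and 0.7. Simulation over the band from 1.3 to the cut-off, which holds about 14% of trials, gave about 7 to 10%, while ANCOVA stayed near 5%. Where the baseline t is near zero, the t-test rejects in less than 5% of trials. Overall, the two-stage rule has a type I error of 4.0 to 4.6%.

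**Step 6: the strata.** If site and OC use together explain 1%, 5% or 10% of the variance of change, power goes from 83.0% to 83.3%, 84.8% or 86.7%. For OC use alone, with 72 users and 148 non-users (11.1), a 2-point difference in mean change explains (72/220) × (148/220) × 2² / 36 = 2.4% of the variance, and power becomes 83.9%. The documents give no site effect.

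**The case against.** The planned test is valid, its power figure is right, and overall type I error is held slightly below 5%. The switch to ANCOVA is written down in advance and depends on baseline values, not on outcomes, so it is not an open choice made after seeing results. The conditional error rates apply to a minority of trials and are offset by the rest. The power gain depends on a correlation and a variance ratio that the documents do not give. The strata add little measurable power.

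All of this stands as a limit on emphasis. There is no false-positive problem overall, the 88 to 95% range is conditional on assumptions, and the strata cannot be argued for mainly on power. None of it defends the rule itself. A baseline significance test remains the wrong trigger, the loss has a clear direction unless the slope is 1, and the stepwise regression does not supply the missing adjustment.

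**Conclusion.** The concern holds. The primary analysis gives up precision that data already being collected would supply. With an SD of change of 6, equal variances and *r* between 0.3 and 0.7, always adjusting for baseline Ki-67 raises power from 83% to between 88% and 95%; the written rule stays at 83 to 84%. The direction is well supported by the entry threshold and the floor at zero, while the size rests on the assumed correlation and variance ratio. The case for site and OC use is agreement with the stratified randomisation and a correct standard error, with a small power gain. The change should be made, but the planned test is not invalid without it.

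**What to change.** Replace the rule in Section 11.2 with one primary model used in all cases: ANCOVA of change in Ki-67 on arm, baseline Ki-67, OC use (yes/no) and site, with small sites pooled by a rule stated in advance. Delete the baseline significance test. Keep the unadjusted t-test as a sensitivity analysis.

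Section 11.2 also has a fallback for skewed data, and pilot Ki-67 was skewed (mean 6.4%, median 4%, Section 3.0). The same amendment should name the transformation or rank-based ANCOVA to be used, and when.

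Report the arm effect within OC users and non-users as a planned secondary, descriptive result. With 72 users split 48:24, the standard error is 6 × √(1/48 + 1/24) = 1.5, so power for 2.5 points is only Φ(2.5/1.5 − 1.96) = 38%.

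The cost is a text amendment before unblinding, through the lead and local IRBs as Section 12.0 requires. It needs no new data and no added patients.
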